## 3.8 Secondary Endpoint Analyses

### 3.8.1 Key Secondary Efficacy Endpoints

The following secondary endpoints will be assessed in a hierarchical manner, comparing EP-104IAR versus vehicle. If the primary endpoint is statistically significant at the 5% level, then the first secondary endpoint may be formally assessed for statistical significance. If the first secondary endpoint is statistically significant at the 5% level, then the second secondary endpoint may be formally tested, and so forth. Upon failure of any inferential test at the 5% level, no subsequent secondary endpoints may be declared to be statistically significant. Analysis of these secondary endpoints will be based on the ITT population. If the PPS population markedly differs from the ITT population as described above, identical analyses for the PPS population will be performed.

The endpoints are as follows:

- Difference in change from baseline between EP-104IAR and vehicle in WOMAC Function at Week 12
  - Analysis will be identical to that described for the primary endpoint.
- Difference between EP-104IAR and vehicle in the area under the WOMAC Pain-time curve to 12 weeks post-dose
  - Area under the curve in change from baseline WOMAC Pain from Week 0 to Week 12 will be calculated on a per-individual basis using the linear trapezoidal rule. AUC will be normalized to account for subjects whose actual days and nominal days at Week 12 differ. Treatments will be compared using an ANCOVA model containing site (possibly grouped, see Section 4.2); individual baseline WOMAC Pain; and treatment group as covariates.
- Difference in change from baseline between EP-104IAR and vehicle in WOMAC Pain at Week 24
  - Analysis will be identical to that described for the primary endpoint.
- Difference between EP-104IAR and vehicle in Outcome Measures in Rheumatology-Osteoarthritis Research Society International (OMERACT-OARSI) strict responders at Week 12
  - The proportion of patients meeting the strict responder definition at Week 12 will be compared (EP-104IAR versus placebo) using Fisher's exact test. Patients who discontinue prior to Week 12 will be considered non-responders.
  - Strict responders, under the OMERACT-OARSI criteria, are defined as  $\geq 50\%$  improvement in WOMAC Pain or Function score and an absolute change  $\geq 2$  in the respective score (scores scaled 0 – 10).

### 3.8.2 Additional Secondary Efficacy Endpoints

All other efficacy data (WOMAC subscales, total WOMAC, NPRS, PtGA, MDGA, SF-36) will be listed and summarized in tables using standard summary statistics by treatment group. Exploratory analyses will be performed to identify key features of the efficacy profile. Analyses of these additional secondary endpoints will be based on the ITT population.

The following additional secondary endpoints will be assessed:

- Difference in change from baseline between treatment groups in WOMAC Pain at Weeks 1-11 and 13-23
  - This analysis will be identical to the primary analysis.
- Difference in change from baseline between treatment groups in WOMAC Pain Q1 (pain on walking) at Weeks 1-24
  - This analysis will be identical to the primary analysis.
- Difference in change from baseline between treatment groups in average daily NPRS at Weeks 1-24
  - This analysis will be identical to the primary analysis.
  - Average daily NRPS at Week 1 is defined as the average of non-missing NPRS pain scores from Day 1 through 8. For subsequent Weeks, average daily NPRS is defined as the average of the 7 days of non-missing daily NPRS data, allowing for the 8 day Week 1 (for example, Week 2 would be Days 9 through 15).
  - Baseline NPRS is defined as the average of the seven non-missing days immediately prior to dosing (Day 1).
- Difference in change from baseline between treatment groups in WOMAC Function at Weeks 4, 8, 16, 20 and 24
  - This analysis will be identical to the primary analysis.
- Difference in change from baseline between treatment groups in WOMAC Stiffness scores at Weeks 4, 8, 12, 16, 20 and 24
  - This analysis will be identical to the primary analysis.
- Difference in change from baseline between treatment groups in WOMAC Total scores at Weeks 4, 8, 12, 16, 20 and 24
  - This analysis will be identical to the primary analysis.
  - WOMAC Total is defined as the average of the three subscale scores (Pain, Stiffness, and Function).
- Difference between treatment groups in time to return to baseline WOMAC Pain

- This will be analyzed using a Cox proportional hazards regression with treatment, site (possibly grouped; see Section 4.2), and baseline WOMAC Pain as covariates. Kaplan-Meier median and quartiles will also be displayed.
- Time to return to baseline is defined as the first week, of two consecutive non-missing weeks, where the WOMAC Pain score is  $\geq$  Baseline. For example, if a subject's WOMAC Pain scores are 5.0 (Baseline) and then:
  - 5.0 (Week 1), 4.8 (Week 2), 5.6 (Week 3), 5.0 (Week 4), 3.0 (Week 5), and 2.8 (Week 6), the return to baseline is Week 3 for this subject.
  - 5.6 (Week 1), 4.4 (Week 2), 4.2 (Week 3), 4.0 (Week 4), 3.0 (Week 5), and 2.0 (Week 6) (and then discontinued), the time to baseline pain for this subject is censored at Week 6.
  - 5.6 (Week 1), 6.0 (Week 2), 5.4 (Week 3), 4.6 (Week 4), and 4.4 (Week 5), the return to baseline is Week 1 for this subject.
  - 4.4 (Week 1), 5.2 (Week 2), Missing (Week 3), 5.6 (Week 4), and 3.2 (Week 5), the return to baseline is Week 2 for this subject.
  - Has 23 consecutive weeks of 2.0, and then 5.2 at Week 24, the time to baseline pain is censored at Week 24.
- Difference between treatment groups in area under the curve (AUC) of WOMAC Pain at Weeks 1–24
  - This analysis will be identical to that described for the key secondary endpoint for AUC of WOMAC Pain.
- Difference between treatment groups in AUC of average daily NPRS at Weeks 1–24
  - This analysis will be identical to that described for the key secondary endpoint for AUC of WOMAC Pain, however no missing data imputation will be done for this endpoint.
  - Average daily NPRS at Week 1 is defined as the average of non-missing NPRS pain scores from Day 1 through 8. For subsequent Weeks, average daily NPRS is defined as the average of the 7 days of non-missing daily NPRS data, allowing for the 8-day Week 1 (for example, Week 2 would be Days 9 through 15).
- Difference between treatment groups in AUC of WOMAC Function, Stiffness and Total scores at Weeks 4, 8, 12, 16, 20 and 24
  - This analysis will be identical to that described for the key secondary endpoint for AUC of WOMAC Pain, however no missing data imputation will be done for these endpoints.
- Difference between treatment groups in OMERACT-OARSI strict responders at Weeks 4, 8, 16, 20 and 24

- This analysis will be identical to that described for the key secondary endpoint for OMERACT-OARSI strict responders at Week 12.
- Difference between treatment groups in PtGA at Weeks 4, 8, 12, 18 and 24
  - This analysis will be identical to the primary analysis.
- Difference between treatment groups in MDGA at Weeks 4, 8, 12, 18 and 24
  - This analysis will be identical to the primary analysis.
- Difference between treatment groups in SF-36 at Weeks 12 and 24
  - Each of the 8 SF-36 domains, as well as the two component scores (Mental and Physical), will be modeled separately using an ANCOVA model with treatment, site (possibly grouped; see Section 4.2), and covariate baseline score as covariates.
  - SF-36 scoring will be directly obtained from the QualityMetric PRO CoRE software.
- Difference between treatment groups in average rescue medication usage at Weeks 1-24
  - The weekly average frequency of rescue medication use will be based on the ePRO diary data. Rescue medication will be considered to be taken on each day where it is recorded that rescue medication was consumed for index knee pain. Weekly averages will be calculated based on actual days in the study. At least 4 non-missing rescue medication diary entries in a week must be available for the weekly average at that week to be calculated. Section 4.3 describes the imputation strategy for instances when less than 4 rescue medication entries are available at a given week. The weekly average frequency of rescue medication use will be analyzed at actual weeks with an ANCOVA model with site (possibly grouped; see Section 4.2), treatment, and baseline (pre-dose) weekly average frequency of rescue medication use as covariates.

Depending on the distribution of the observed data, the weekly average frequency of rescue medication use may be transformed appropriately prior to fitting the model.

- The average daily dosage (mg) of rescue medication will be based on information from the rescue medication accountability eCRF pages only. Average daily dosage (mg) of rescue medication will be calculated between each observed scheduled visit. This will be calculated by multiplying 500 mg by the number of tablets within a bottle consumed divided by the number of days between visits associated with the bottle. Note that at each visit, rescue medication is returned and accounted for from the previous observed visit and new medication is potentially both dispensed and re-dispensed. It will be assumed that rescue medication taken on the day of return/dispensing will be from the newly dispensed/re-dispensed medication. For a

	EP-104IAR-201 Statistical Analysis Plan	Version: Final 1.0
	Date: 14-Jun-2023	Page 23 of 38

given observed visit, the number of days between visits will be calculated as: start date of current visit – start date of previous visit. If an interim visit is missing but dispensing and return information is provided at the previous and later visits, then rescue medication usage at the later visit will be calculated according to the period between the two observed visits. The number of tablets consumed will be calculated from the eCRF data as: number of tablets dispensed/re-dispensed – number of tablets in returned kit – number of tablets not accounted for. If a subject marks “unknown” for number of not accounted for tablets, then the number of consumed tablets cannot be calculated and, therefore, the average daily dose of rescue medication for that period will be considered missing. Rescue medication may be calculated for following visits if all dispensing and return information is provided for those periods. If no medication is dispensed at a given visit, then no medication is assumed to have been taken between that visit and the next or until new rescue medication is dispensed, if any. If this occurs, then the daily average dosage (mg) will be considered 0 while the subject is in the study.

The average daily dosage (mg) will be analyzed at each post-baseline scheduled visit with an ANCOVA model with site (possibly grouped; see Section 4.2, treatment, and baseline average daily dosage (mg) as covariates.

- Difference between treatment groups in average activity levels at Weeks 1-24
  - This analysis will be analogous to the average rescue medication endpoint above.
  - Average daily activity level will be transformed to a 0-1 scale, where 0=Low, 0.5=Moderate and 1=High.
- Difference between treatment groups in WOMAC Pain responder categories at Week 4, Week 8, Week 12, Week 18, and Week 24
  - Subjects will be considered to be an X% responder if they have at least an X% decrease from baseline WOMAC Pain.
  - Separate summaries for 30% response, 50% response and 70% response will be presented. Each summary will be done by time point and treatment, and will include the number of subjects with data, the number and percentage of responders as well as the P-value from Fisher’s exact test comparing proportions of responders between treatment and vehicle.

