Design	
A randomized, double-blind, vehicle-controlled parallel-group study.
 
Qualified subjects will be administered a single IA dose of 25 mg EP-104IAR or vehicle and will be followed up for up to 24 weeks. The study involves 10 site visits. The maximum duration of participation per subject ≈ 32 weeks (up to 6 weeks Screening, 2 weeks Washout and Baseline and 24 weeks Follow-up). Participation in the optional imaging sub-study extends the maximum duration per subject to ≈ 60 weeks with additional magnetic resonance imaging (MRI) site visits.
 
Data Collection
 
The primary means of data collection will be via an electronic patient-reported outcome (ePRO) device. Subjects will be provided with a hand-held device programmed to prompt the subject to record data as required throughout the study as follows:
 
Daily:
 
 • 11-point Numeric Pain Rating Scale (NPRS, 0-10 scale where 0 = no pain and 10 = worst pain imaginable), measured each evening, e.g., “How was your pain level in your (right/left) knee over the past 24 hours?”. • Question on rescue medication use (24-hour recall), e.g., “Did you use any of the provided rescue medication over the past 24 hours?” (Yes/No). • If yes, question on whether rescue medication was used to treat pain in the Index knee, e.g., “Did you use the provided rescue medication to treat pain in your affected knee?” • Question on use of other pain medications, e.g., “Did you use any other pain medications over the past 24 hours for any reason?” (Yes/No).

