9.1.7.2 NPRS – Numerical Pain Rating Scale

Subjects will rate their daily Index knee pain throughout the study using the NPRS. During the Washout and Baseline Period this question will be asked separately for each knee. From Visit 2 onwards NPRS scores will only be collected for the Index knee. Subjects will enter scores each **evening** directly into the ePRO device provided.

[figure not shown]
The question for the subject is: “How was your pain level in your (right/left) knee over the past 24 hours?

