9.2.4 Visit 2: Baseline and Dosing (Day 1)

9.2.4.1 Pre-Dose Procedures

Subjects will return to the site once the Washout and Baseline Period is complete. Subjects will be required to bring their ePRO device and any unused rescue medication to the site.

Following review of eligibility and Index knee selection, qualified subjects will be randomized to receive a single IA injection of EP-104IAR or vehicle control in their Index knee.

In addition to confirming eligibility, **pre-dose activities** include:

- Blood samples for hematology, clinical chemistry, cortisol and PK analyses.
- Urine collection for safety urinalysis, pregnancy test and drugs of abuse.
- Vital signs.
- Physical exam.
- Exam of Index knee.
- Weight.
- PtGA.
- MDGA.
- WOMAC Index.
- Health status (SF-36).
- Recording changes in procedures or conmed use.

Imaging Sub-Study

Subjects who volunteer to participate in the imaging sub-study will have a separate visit for baseline MRI to be performed prior to all pre-dose activities listed above.

The baseline MRI can occur on a separate day but must be within 5 days before dosing.

For women of childbearing potential, the pre-dose urine sample for pregnancy testing will be collected prior to the baseline MRI to confirm eligibility for the MRI scan. This does not need to be repeated prior to dosing

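### The Week 1 NPRS average includes the dosing day, part of whose 24-hour recall is pre-dose pain, and this modestly attenuates the Week 1 treatment difference

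*SAP*

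**What the plan says.** - **Week 1 window.** In the change-from-baseline endpoint for daily NPRS, SAP 3.8.2 takes Week 1 as "the average of non-missing NPRS pain scores from Day 1 through 8". The NPRS AUC endpoint in the same section repeats the rule: Week 1 "is defined as the average of non-missing NPRS pain scores from Day 1 through 8".
- **Later windows.** Each later week has seven days: "for example, Week 2 would be Days 9 through 15".
- **Baseline.** SAP 3.8.2 and 4.1 take baseline NPRS from the seven days before dosing, so Day 1 is not in it.
- **The score.** Protocol 9.1.7.2 asks "How was your pain level in your (right/left) knee over the past 24 hours". The Synopsis and 9.1.7.2 place the entry in the evening, with no clock time.
- **Dosing.** Protocol 9.2.4 puts dosing at Visit 2, Day 1. The pre-dose list in 9.2.4.1 includes "Blood samples for hematology, clinical chemistry, cortisol and PK analyses", and Protocol 9.1.5.1.1 requires serum cortisol to be drawn between 7 and 11 a.m. No clock time is given for the injection.
- **Sparse diaries.** SAP 4.3 brings a post-baseline week with fewer than four diary entries up to four by carrying forward the most recent post-baseline entries. For the NPRS AUC endpoint, SAP 3.8.2 says that no missing-data imputation is done.
- **Status.** Both NPRS endpoints are additional secondary endpoints, outside the hierarchy in SAP 3.8.1.

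**The concern.** The Day 1 entry looks back from the evening after the injection to the evening before it, so it mixes pre-dose and post-dose pain in every subject. Using the same rule in both arms does not make it neutral. Pre-dose pain has no expected treatment difference, and an average that includes it understates the difference produced by the post-dose days.

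What is at stake is the estimate of early effect on the trial's only daily pain measure: the Week 1 NPRS contrast and the first part of the cumulative NPRS AUC. The documents present rapid onset as a Phase 1 finding (Protocol 1, SAP 1.1), so Week 1 is a time point that readers will look at.

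**Working it through.** The plan gives no figure for this effect, so the first step is to reproduce its calendar. Week 1 is Days 1–8, and week *k* ≥ 2 is Days 7*k* − 5 to 7*k* + 1. That gives Days 9–15, 16–22, … 163–169, and 8 + 23 × 7 = 169 days. Only Week 1 has eight days, and every window ends on the nominal target day.

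**Step 1. Pre-dose share of the Day 1 recall.** Share = 1 − (entry hour − dosing hour)/24. The clock times are assumptions. The pre-dose cortisol draw suggests morning to midday dosing, so I take dosing at 08:00–14:00 and entry at 18:00–23:00.

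| Dosing | Entry 18:00 | Entry 20:00 | Entry 23:00 |
|---|---|---|---|
| 08:00 | 58.3% | 50.0% | 37.5% |
| 10:00 | 66.7% | 58.3% | 45.8% |
| 12:00 | 75.0% | 66.7% | 54.2% |
| 14:00 | 83.3% | 75.0% | 62.5% |

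Over the full hourly grid (7 × 6 = 42 combinations) the share exceeds 50% in 32, equals 50% in 4 and is below 50% in 6. The last group is early dosing with a late entry.

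**Step 2. Attenuation of the Week 1 difference.** Let δ be the average daily difference over the other days of Week 1, and let Day 1 carry *q*δ. With *m* entries including Day 1, the retained fraction is (*m* − 1 + *q*)/*m*, so the attenuation is (1 − *q*)/*m*.

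Full diary, *m* = 8:
- Effect proportional to post-dose hours: *q* runs from 4/24 = 0.167 to 15/24 = 0.625. Attenuation runs from (1 − 0.167)/8 = 10.4% down to (1 − 0.625)/8 = 4.7%.
- Gradual onset, linear over *r* days: Day *k* ≥ 2 carries min(1, (*k* − 0.6)/*r*) and Day 1 carries 0.4 × min(1, 0.4/*r*). Attenuation is 10.5% for *r* = 1, 11.8% for *r* = 3 and 12.0% for *r* = 7.
- No effect on Day 1, *q* = 0: 1/8 = 12.5%, the ceiling under these models.

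Sparse diary, *m* = 4 including Day 1: attenuation is up to 1/4 = 25% for the subjects concerned. Week 1 has no earlier post-baseline week to borrow from.

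**Step 3. Does the eighth day buy precision?** With a constant within-week correlation ρ (an assumption), the variance of a mean of *m* days is proportional to (1 + (*m* − 1)ρ)/*m*. The ratio of SDs, eight days to seven, is 0.992 at ρ = 0.5, 0.996 at 0.7 and 0.999 at 0.85. The gain is under 1%, so it does not offset a loss of 5% or more.

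**Step 4. NPRS AUC.** Assume change from baseline is zero at Week 0, a constant difference from Week 1 on, linear trapezoids, and the worst case *q* = 0. In units of δ × weeks, the true AUC to Week *T* is *T* − 0.5. The Week 1 shortfall of 0.125 has weight 0.5 at *T* = 1 and weight 1 afterwards.

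- Week 1: 0.0625/0.5 = 12.5%
- Week 2: 0.125/1.5 = 8.3%
- Week 12: 0.125/11.5 = 1.1%
- Week 24: 0.125/23.5 = 0.5%

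**Step 5. Later weeks.** No window from Week 2 on contains Day 1. The one route into them is SAP 4.3: if Day 1 counts as post-baseline, it could be carried into a sparse Week 2 for a subject with few Week 1 entries.

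**The case against.** The strongest reply is that the rule is pre-specified, treats the arms alike, counts every entry from dosing onward and ends each window on its nominal day. Its bias works against the test product, so it cannot create a false positive. The endpoint is not in the testing hierarchy. Early pain relief is also measured by weekly WOMAC Pain, whose Week 1 score maps to Days 7–13 (SAP 4.1) and whose 24-hour recall therefore does not reach Day 1. All of this stands, and it is why the point is minor. It does not show that the eight-day average is the better estimate of the Week 1 effect. Days 2–8 also ends on Day 8.

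Four stronger readings are tempting, and the documents do not support them:

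- **That the Day 1 score is mostly pre-dose, as a fact.** This is an inference from the cortisol window and the evening entry. It holds for most plausible clock times and fails for early dosing with late entry. Only the presence of some pre-dose recall is certain.
- **That the Week 1 difference is cut to seven eighths.** That is the full-diary case with no Day 1 effect, not the expected case.
- **That the 1.6-point Week 1 difference from Phase 1 (Protocol 1.2.2) would read as 1.4 here.** The documents do not say which days or what recall that score covered, and the study had 32 subjects and a 15 mg dose. It may already include the dosing day.
- **That Week 1 was lengthened in order to capture the Day 1 score.** The SAP gives no reason for the eight days.

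**Conclusion.** The point holds, at low severity. The Week 1 NPRS average contains a score that is partly pre-dose in every subject, and this biases the Week 1 difference toward zero. The attenuation is about 5% to 12.5% with a full diary, and up to 25% for a subject with only four entries including Day 1. NPRS AUC is affected materially only in the first weeks.

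The sizes rest on assumed clock times for dosing and entry, on an assumed onset pattern within Week 1 and, for the AUC, on a constant effect thereafter. The direction rests only on randomization and the 24-hour recall. Type I error is not inflated, and no primary, key secondary or weekly WOMAC Pain result changes.

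**What to change.** In both places in SAP 3.8.2 where Week 1 NPRS is defined (change from baseline, and AUC), replace Days 1–8 with Days 2–8. Delete the clause in each that allows for an eight-day first week. Keep Week 2 as Days 9–15 and all later windows as they are.

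Add one sentence, in SAP 3.8.2 or 4.3, that the Day 1 NPRS entry does not count as post-baseline for weekly averaging or for carry-forward. Baseline already excludes Day 1 and needs no change. The entry can still be listed.

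The cost is a few words in the SAP: no new data, no change to any other window, and under 1% in the SD of the Week 1 average. If the definition can no longer be changed before unblinding, report Days 2–8 as a labelled sensitivity analysis for Week 1 NPRS and the early NPRS AUC.

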#### 3.2 Randomization

Eligible subjects will be randomly assigned to treatment and vehicle in a 1:1 allocation ratio.

 PROSOFT Clinical	EP-104IAR-201 Statistical Analysis Plan	Version: Final 1.0
	Date: 14-Jun-2023	Page 15 of 38

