### 3.3 Sample Size Considerations

This study has been sized making the following assumptions:

- Inferential testing is at the (two-sided) 5% level, and with a desired power of 80%.
- The primary endpoint is the difference between treatment groups in change from baseline WOMAC Pain (average of 5 pain items) at 12 weeks post-dose, as measured using a 0-10 scale
- The standard deviation of the endpoint is 2.2, as assessed from review of similar studies from clinicaltrials.gov
- The desired difference to detect is 0.8.

Based on these assumptions, a sample size of approximately 120 subjects per treatment group is required. Assuming a drop-out rate of approximately 20%, 150 subjects will be randomized and dosed in each treatment arm.

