### 3.7 Primary Endpoint Analysis

The primary efficacy endpoint is the difference in change from baseline between EP-104IAR and vehicle in WOMAC Pain at Week 12, in the ITT population. Baseline WOMAC Pain will be calculated at the individual level and is defined as the average of no more than three pre-dose measurements including the three scheduled measurements: 2 measurements during the Washout and Baseline Period and 1 at Visit 2 (pre-dose). If the subject has less than three pre-dose measurements, the average of all available pre-dose measurements will serve as the subject's baseline value. If a subject has more than three pre-dose measurements, then the three measurements collected immediately prior to pre-dose will be used to derive baseline WOMAC pain and earlier measurements will not contribute.

Change from individual pre-dose baseline will then be calculated for each post-dosing weekly assessment from Week 1 through Week 24. A mixed-effects model for repeated measures (MMRM) model will then be fit to the change from baseline data for all subjects in the ITT population, including fixed effects terms for: site (potentially grouped, see Section 4.2 for more details); individual baseline WOMAC Pain; and the treatment-by-week interaction, where treatment and week are both defined as categorical variables. A random per-patient intercept will also be included. An unstructured covariance matrix at the patient level will initially be fit; if this model fails to converge numerically, a compound symmetry structure will be used.

No imputation of missing data will be performed for this analysis; the MMRM model allows handling of missing data under the assumption that data is missing at random (MAR). To assess robustness to the assumption that data is missing at random, a multiple imputation approach will be used. Under this approach, outcome data will be imputed according to the following logic:

	EP-104IAR-201 Statistical Analysis Plan	Version: Final 1.0
	Date: 14-Jun-2023	Page 18 of 38

- If missing data is due to lack of efficacy (as captured by the Study Termination page on eCRF), data will be imputed as if subjects received placebo.
- If missing data is due to other reasons, data will be imputed as if subjects received their actual treatment.

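### Time to return to baseline pain censors subjects who leave for lack of efficacy on an unconfirmed return, which biases each arm's Kaplan-Meier duration upward

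*SAP*

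**What the plan says.** **Event.** SAP 3.8.2: "Time to return to baseline is defined as the first week, of two consecutive non-missing weeks, where the WOMAC Pain score is" at or above baseline. The analysis is a Cox model with treatment, site and baseline WOMAC Pain, plus Kaplan-Meier median and quartiles.

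**Worked examples.** Two of the five matter here, both with baseline 5.0.
- The discontinuation example falls steadily to 2.0 at Week 6, gives no reason for stopping, and ends "and then discontinued), the time to baseline pain for this subject is censored at Week 6".
- The Week 24 example has 23 weeks at 2.0 and then 5.2 at Week 24. It is censored at Week 24.

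No rule for this endpoint depends on the reason for discontinuation, and no sensitivity analysis is given.

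**Elsewhere in the SAP.** The robustness analysis in SAP 3.7 separates these leavers: "If missing data is due to lack of efficacy (as captured by the Study Termination page on eCRF), data will be imputed" as though they had been on placebo. In SAP 3.8.1, subjects who discontinue before Week 12 are strict non-responders.

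**Early-exit scores.** Protocol 5.4 and 9.2.6 ask early leavers to complete the Visit 9 assessments, which include WOMAC (Protocol 9.2.5.7). SAP 4.4 classes early-exit visits as unscheduled and allows their data only for baseline. SAP 3.1 exempts WOMAC from the scheduled-assessment rule, and SAP 4.1 assigns WOMAC scores to weeks by actual study day.

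**The concern.** Kaplan-Meier and Cox methods assume that a censored subject has the same later risk as those still under observation. Someone who leaves for lack of efficacy just after pain has climbed back to baseline plainly does not. The reason for leaving is already on the Study Termination page, and SAP 3.7 treats it as informative.

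The rationale for the higher dose is longer duration (Protocol 2 and 2.1; SAP 1.3). This is the only time-to-event efficacy endpoint that either document lists, so its median and quartiles are natural figures to quote for duration.

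**Working it through.** **1. The plan's own figures.** The documents state no event count, median, hazard ratio or power for this endpoint. The sample size in SAP 3.3 reproduces: n = 2 × (1.960 + 0.842)² × 2.2² / 0.8² = 118.7, so 119 per arm (119.7 with the t distribution; 120 stated), and 120 / 0.80 = 150. It concerns the primary endpoint only. The one usable input here is "Assuming a drop-out rate of approximately 20%, 150 subjects will be randomized and dosed in each treatment arm": 0.20 × 150 = 30 leavers per arm, for all causes.

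**2. Applying the rule.** Coded as written, it reproduces all five examples: event at Week 3, censored at 6, event at 1, event at 2, censored at 24. Two further subjects with baseline 5.0 show the gap:
- Scores 3.0, 3.5, 4.0, 4.4, 4.8, 5.6, then leaves: censored at Week 6, although the last score is above baseline.
- Scores 3.0, 3.5, 4.0, 4.4, 4.7, 4.8, then leaves: censored at Week 6, correctly, because the event has not occurred.

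**3. Size within one arm.** Assume a true median of m weeks with constant weekly hazard h = 1 − 0.5^(1/m). Assume also that a share q of true returners leave for lack of efficacy at their first score at or above baseline. Neither m nor q is in the documents. The rule then sees hazard h(1 − q), and the Kaplan-Meier median is ln 0.5 / ln(1 − h(1 − q)), roughly m / (1 − q). For m = 14 and q = 20%: h = 0.0483, h(1 − q) = 0.0386, median 17.6.

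| True median (weeks) | q = 5% | q = 10% | q = 20% | q = 30% |
|---|---|---|---|---|
| 10 | 10.5 | 11.2 | 12.6 | 14.4 |
| 14 | 14.8 | 15.6 | 17.6 | 20.2 |
| 18 | 19.0 | 20.0 | 22.6 | 25.9 (beyond Week 24) |

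For m = 14, the week by which 25% have returned moves from 6 to 7, 7 and 8 at q = 5%, 10% and 20%.

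**4. A ceiling on q.** With m = 14, the share with a first return by Week 23 is 1 − 0.5^(23/14) = 0.68, or about 102 of 150. If all 30 assumed leavers were of this kind, q would be 30 / 102 = 29%. Drop-out has other causes too, so under the plan's assumption q should be well below that.

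**5. Between arms.** In this model the hazard ratio under the rule is about HR × (1 − q_EP) / (1 − q_vehicle). The simulated values come from 300 trials of 150 per arm with true medians of 18 and 12 weeks. The hazard ratio is about 0.67 when the exit counts as the event.

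| q, EP-104IAR | q, vehicle | Formula | Simulated, SAP rule |
|---|---|---|---|
| 20% | 20% | 0.67 | 0.67 |
| 5% | 20% | 0.80 | 0.80 |
| 20% | 5% | 0.56 | 0.56 |

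**6. A second simulation.** This used 20,000 subjects per arm and assumed pain trajectories: baseline mean 6 (SD 1.2), between-subject SD 1.6, autocorrelation 0.7, residual SD 1.0. Each week at or above baseline carried an assumed exit probability. Kaplan-Meier share returned by Week 24, SAP rule vs exit counted as event:

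| Weekly exit probability | EP-104IAR | Vehicle | Gap between arms (points) |
|---|---|---|---|
| 5% | 23.2% vs 25.2% | 34.3% vs 36.8% | 11.1 vs 11.6 |
| 10% | 21.4% vs 25.2% | 32.1% vs 37.2% | 10.7 vs 12.0 |
| 20% | 19.0% vs 26.7% | 28.6% vs 38.7% | 9.6 vs 12.0 |

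The first two rows correspond to 8% and 14%, then 13% and 21%, leaving for lack of efficacy (EP-104IAR, vehicle). That 21% already exceeds the plan's 20% for all causes. The cumulative-hazard ratio, ln(1 − EP) / ln(1 − vehicle), is 0.63 vs 0.63, 0.62 vs 0.62 and 0.63 vs 0.63.

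**The case against.** A reader might infer that the rule records failures as continuing benefit and so overstates EP-104IAR's duration against vehicle. The documents do not support that. Censoring removes a subject at the last score and assigns the later hazard of those who remain; it does not record benefit to Week 24. In the second simulation only 21% to 43% of lack-of-efficacy leavers were censored, so 57% to 79% already counted as events. The gap between arms shrank slightly under the SAP rule and the cumulative-hazard ratio hardly moved. If vehicle subjects leave more often on an unconfirmed return, the rule works against the product.

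Other points in the plan's favour stand in part:
- The primary mixed model also assumes missing at random. Placebo-based imputation in SAP 3.7 is a robustness check, so the gap here is a missing companion analysis and not a contradictory main rule.
- Confirmation by a second score guards against week-to-week noise, and some single high scores would not have been confirmed.
- Such exits may be few: this is a single-dose trial, rescue is allowed throughout (Protocol 7.5), and retention is preferred (Protocol 5.4).
- Duration is also assessed by WOMAC Pain at Week 24 (a key secondary endpoint), at Weeks 13 to 23, by area under the curve to Week 24, and by strict responders to Week 24.
- In the second simulation 19% to 39% had returned by Week 24, so no median was reached. The median may not be the figure reported.

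These limit the importance. None supplies a rule for an unconfirmed return followed by a lack-of-efficacy exit.

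**Conclusion.** The point holds as a within-arm bias. That such a subject is censored follows from the event definition and the Week 24 example. The discontinuation example alone does not show it. If these exits occur, each arm's Kaplan-Meier time to return is too long: by about 5% to 25% at the median for q between 5% and 20%, under a constant hazard and assumed q. The true size cannot be found from the documents. The hazard ratio is unaffected when q is equal in the two arms and otherwise moves either way.

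Whether an early-exit score could supply the confirmation is unsettled, because SAP 4.4 excludes it while SAP 3.1 and 4.1 place WOMAC scores by study day. Importance is modest: this is an additional secondary endpoint with no alpha-controlled claim.

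**What to change.** Keep the endpoint definition and the all-censored analysis. Before unblinding, pre-specify two analyses to be reported beside it:

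1. Count a discontinuation for lack of efficacy (Study Termination page) with the last score at or above baseline as a return at that week.
2. As a sensitivity analysis, count every lack-of-efficacy discontinuation as an event at the last assessed week. Label it a composite of return to baseline or lack-of-efficacy discontinuation, because it includes subjects still below baseline who have not met the event as defined.

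Other reasons for leaving stay censored in both. Also reconcile SAP 4.4 with SAP 3.1 and 4.1 by stating whether an early-exit WOMAC score that maps to a later week can confirm a return.

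The cost is SAP wording and a little more derivation and analysis work, with no new data. The reported duration may become shorter.
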